## OVERVIEW

### **Objectives**

The purpose of this study is to determine how to best implement appropriate genetic testing and follow-up care in the primary care setting.

**Aim 1:** Compare two strategies for identifying members of a primary care clinic's population who have a family or personal history of cancer and encouraging these high-risk individuals to obtain genetic testing for cancer susceptibility mutations. The two methods are: 1) Point of Care (POC) approach, completed in conjunction with a regularly scheduled appointment; and 2) Direct Patient Engagement (DPE), using letters and emails. Individuals will be asked to visit a web site for screening for family/personal history of cancer. Genetic testing will be recommended for those determined to be high risk. Outcomes will be the fraction of the clinic population that participates in the family/personal screening and the fraction of the clinic population that undergoes genetic testing.

Hypothesis 1: DPE screening will result in a higher proportion of active patients who screen for familial cancer risk compared with POC screening.

Hypothesis 2: Of screened patients, POC patients will produce a higher proportion of tested patients compared with DPE.

**Aim 2:** Identify changes, problems, and inefficiencies in clinical flow and interactions during and after the implementation of genetic testing.

**Aim 3:** Evaluate the effects of the two methods of implementation on patient, provider, and health system leader reports of benefits and harms, satisfaction, and perceived quality of care.

**Aim 4:** Evaluate the value (cost-effectiveness) and affordability (budget impact) of each method.

### **Study Design**

This is a mixed-methods study with randomization at the clinic level, assessment of an implementation approach, and a longitudinal observational component.

### **Background**

Preventing cancer mortality through primary prevention activities is an understudied and important area of research. One method of preventing cancer mortality is to engage women and men in genetic testing, to better enable risk stratification and subsequent targeted cancer prevention/surveillance. Identifying patients with high genetic risk for breast, ovary, colon, or other cancers has important ramifications for an individual's healthcare and is recommended in multiple guidelines for high-risk patients. However, genetic risk is often not identified until after a cancer diagnosis due to barriers at several levels. National data suggests that relatively little population-based implementation of clinical genetic testing currently occurs. Provider barriers include inadequacies in hereditary risk recognition, challenges in making patient referrals, and availability of genetic professionals to provide in-depth counseling. Patient barriers include limited knowledge of testing, financial burdens, and inadequate access to specialty genetic testing services. Studies to date of the implementation process have been conducted in urban, high resourced facilities, under optimal conditions, often not at the clinic or system level. We propose to compare the processes and outcomes of two methods of offering testing and to evaluate follow-up care, quality of life, and economic considerations. We also propose to follow

more intensively the patients that test positive for mutations to understand reactions to difficult medical genetic information.

## **PARTICIPANTS**

### **Participants**

12 primary care clinics will be recruited for the study. The clinics will be a mix of urban and rural locations that are part of either the Billings Clinic or the MultiCare Health System.

Patients involved will be age 25 or older and considered active patients at a participating clinic.

Providers, clinic staff, and at least one clinic leader from each clinic will also be included. These individuals will be age 18 or older and employed by the clinic or healthcare system.

### **Inclusion Criteria**

Primary care clinics will be selected with the help of representatives from the Billings Clinic and the MultiCare Health System. The clinics must be primary care settings that are geographically distinct (no patient/provider overlap) with at least 100 active patients and a volunteer contact/champion.

#### **Inclusion criteria for Aim 1**

Patients included in Aim 1 must be age 25 or older and considered an active patient at one of the participating clinics (i.e., had at least one visit in the past 12 months). They must also be comfortable reading and writing in English.

Half of the clinics will be randomized into the Point of Care (POC) arm. For these clinics, patients will be approached at the time of their visit and invited to complete the risk assessment questionnaire to be included in the study. It is expected that some patients will not have time to complete the assessment, but all patients who meet the criteria above (25 or older, comfortable reading and writing in English; the current appointment qualifies them as an active patient) and could potentially have time to complete the assessment will be approached.

The remaining half of the clinics will be randomized into the Direct Patient Engagement (DPE) arm. For these clinics, all patients who meet the criteria above (25 or older, active patient, comfortable reading and writing in English) will receive a letter and/or email inviting them to complete the risk assessment questionnaire.

#### **Inclusion criteria for Aim 3**

Patients included in Aim 3 must be age 25 or older and considered an active patient at one of the participating clinics (i.e., had at least one visit in the past 12 months). They must also be comfortable reading and writing in English. In addition, patients who test positive for one or more mutations for cancer risk will be followed at an increased schedule to determine any harms due to testing, as well as benefits.

Providers, clinic staff, and the clinic leader from each clinic must be employed by the clinic or healthcare system, 18 years of age or older, and comfortable reading and writing in English. When they complete the baseline survey, they will be asked if they would be willing to do a phone interview. A random sample of those who agree to be interviewed will be contacted.

#### Inclusion Criteria for Aim 4

Providers, clinic staff, and the clinic leader from each clinic must be employed by the clinic or healthcare system, 18 years of age or older, and comfortable reading and writing in English.

#### Exclusion Criteria

N/A

#### Number of Subjects

As the clinics participating in the study have not yet been selected and we do not yet know how many patients would be considered “active” at each clinic, we are not able to estimate the total number of individuals who will be in the study.

We will recruit a total of 12 clinics.

We plan to consent approximately 6,000 patients (to complete surveys and interviews).

We plan to consent approximately 250 providers, clinic staff, and clinic leaders.

We estimate that approximately 200,000 patients will have the opportunity to complete the risk assessment questionnaire and around 3,000 will complete the genetic testing.

Of the patients who complete genetic testing, we anticipate that approximately 200 will participate in a previvor assessment and intervention (described below) because they test positive for one or more mutations.

### **NON-UW RESEARCH SETTING**

#### Reason for Locations

We approached primary care clinics in the Northwest, using existing connections with ITHS. The clinics had to have staff members interested in this research project and be agreeable to the proposed engagement activities. We were also looking for clinics from two different healthcare systems and a mix of urban and rural locations, to make results more widely applicable.

### **RECRUITING and SCREENING PARTICIPANTS**

#### Recruitment and Screening

Primary care clinics will be identified and approached by representatives of the Billings Clinic and the MultiCare Health System. The clinic will need to have a staff member willing to champion the study and assist with implementation. We will also be looking for a mix of urban and rural locations.

#### ***Aim 1***

To compare two strategies to identify and test high-risk individuals within primary care clinics, the 12 clinics will be randomized such that half will use the first method and half will use the second.

##### Point of Care (POC)

For clinics in the POC arm, patients with a clinic appointment will be approached either in person or over the phone by designated clinic staff (e.g., medical assistant, receptionist). The clinic staff will determine whether a patient should be approached by reviewing their EMR, using the eligibility criteria defined in section 2.2.

##### Direct to Patient Engagement (DPE)

For clinics in the DPE arm, we plan to reach out to every patient that meets the eligibility criteria defined in section 2.2. This outreach will be done using mail and email communication. Contact information will be pulled from the EMR by the clinic staff or a healthcare representative. Outreach materials will clearly state the role of the clinic in the study and as the source of the patient's contact information.

#### **Aim 3**

A random sample of active patients will be selected from each clinic and asked to complete a baseline survey. This sample will come out of the list of patients who meet the eligibility criteria defined in section 2.2. The clinic or a healthcare system representative will pull the contact information for the selected patients from their electronic medical record (EMR). The study staff will reach out using mail and email. Outreach materials will clearly state the role of the clinic in the study and as the source of the patient's contact information (see attached Study Recruitment Templates). This process will be repeated approximately 12 months later, to obtain a second snapshot of the patient population.

We are also interested in interviewing patients who have reached various stages in the risk assessment and genetic testing process. The patient names and contact information will be obtained by clinic staff or directly from the patient through the risk assessment survey.

For previvors (patients who test positive for one or more mutations) we receive the results from Color Genomics from patients who have agreed to allow Color to share their results and we implement the previvor assessment and intervention procedures, using email and telephone.

Providers, clinic staff, and clinic leaders at each clinic will be identified by a representative at the clinic. All of these individuals will be contacted. Contact information will come from the clinic's employee directory or a similar source. Outreach will be conducted using mail and email and will clearly state the role of the clinic in the study and as the source of the individual's contact information (see attached Study Recruitment Templates). A random sample of those who agree to be interviewed will be contacted for an interview.

#### **Aim 4**

This aim will include the providers, clinic staff, and clinic leaders at each clinic that were identified in Aim 3. All of these individuals will be contacted. Contact information will come from the clinic's employee directory or a similar source. Outreach will be conducted using email to complete a longitudinal survey. Emails will be collected at the end in order to follow-up.

#### **Recruitment Materials**

Individuals invited to participate in the surveys and interviews will receive a letter and/or email introducing the study.

Patients visiting clinics in the POC arm will be given a tablet with the risk assessment website loaded (in-person visits), or walked through the risk assessment over the phone by a clinic staff member. A document with examples of talking points has been uploaded into Zipline. Patients in the POC arm may be approached by clinic staff that they are familiar with from previous visits to the clinic.

Patients in the DPE arm will receive a letter and email (for those who have an email address) introducing the study and providing a link to the study website.

Previvors will receive a phone call from study staff to explain the purpose of the previvor assessment. In this call, study staff will explain the purpose of the call, their role, and a brief overview of the assessment and an invitation to complete an interview in conjunction with the assessment. Study staff will empathize the patient's participation in the assessments and interviews is voluntary. The recruitment email, if patient is not contactable by phone, will have similar language. Both forms of outreach will give the study and a local clinic contact's contact information for patient's reference. If patient wishes to proceed, they will be sent a link to the REDCap survey to fill out the assessment and informed a study staff member will follow up to schedule an interview when they have had a chance to complete the assessment.

### **Payment to participants**

Participants will be compensated for survey and interview time using gift cards provided by the research team. They will receive the gift cards (\$50 for providers and clinic leaders in Aim 3, \$10 for patient surveys and baseline previvor interviews, \$20 for patient follow-up previvor interviews, and \$10 for providers, staff and clinic leaders in Aim 4) within a month after each completed interview or survey.

The typical amount a patient would receive is \$10 (for completing a single survey). The typical amount a provider would receive is \$50 (for completing a single survey). The greatest total amount a participant could receive is \$240 (a provider completing the baseline survey and interview, at \$50 each, the follow-up survey and interview, at \$50 each, and all 4 economic surveys, at \$10 each).

### **Non-monetary compensation**

High risk patients will receive genetic testing at no cost to them and those who complete the testing will have access to free genetic counseling. Providers and staff will have access to free CME credits as part of completing training provided by the study.

## **PROCEDURES**

### **Study Procedures**

We propose a clinic-level randomized trial to evaluate two methods of engaging patients in population-based testing for cancer risk.

### **Baseline Assessment**

Before randomizing the clinics, a baseline assessment will be completed.

Clinics: The clinics will be asked to provide aggregate data that will be used to describe their patient population.

Patients: A random sample of patients will be selected from each clinic and asked to complete a baseline survey. This baseline survey will take approximately 20 minutes to complete and will be done online or on paper. Reminders to complete the survey will be sent by email and/or mail.

Providers and clinic staff: Providers and staff at the clinics will be asked to complete a baseline survey online or on paper. A subset will be asked to complete an interview. Interviews will be performed over the phone and will be recorded so that the transcripts can be analyzed.

### Randomization of clinics

Once the baseline assessment is complete, randomization will occur at the level of the clinic (within healthcare system). We will block on healthcare system and clinic size to help ensure comparable arms.

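### Clinic allocation is balanced on health system and size but not on urban/rural location, a feature the plan deliberately mixes, so one draw of 12 clinics may well leave the arms uneven on it

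*Combined protocol and SAP*

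**What the plan says.** On selection, the Participants section states: "The clinics will be a mix of urban and rural locations that are part of either the Billings Clinic or the MultiCare Health System". Recruitment and Screening repeats the aim, and Reason for Locations gives its purpose: "a mix of urban and rural locations, to make results more widely applicable". The Background section also criticises earlier implementation studies for being done in urban, well-resourced facilities.

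On allocation, the Aim 1 recruitment section says "the 12 clinics will be randomized such that half will use the first method and half will use the second". Randomization of clinics places the draw within healthcare system, after the baseline assessment, and adds: "We will block on healthcare system and clinic size to help ensure comparable arms". Rurality is not listed. Block sizes and size categories are not given.

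On what is known before the draw, Baseline Assessment says "The clinics will be asked to provide aggregate data that will be used to describe their patient population", and this comes before randomisation.

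On analysis, the Statistical Analysis Plan takes the clinic as the unit for the primary outcomes. It plans logistic regression with a scale adjustment for overdispersion, then multivariable logistic regression, and it mentions additional site-level data. It names no covariate.

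**The concern.** Urban or rural location is the clinic feature that the plan goes out of its way to vary, but its distribution between arms is left to chance unless system or size happens to carry it. Both engagement methods depend on access. Point of Care needs a visit or a telemedicine contact. Direct Patient Engagement needs post, email and an online tool. It is a reasonable judgement that reach by either route could differ between urban and rural clinics, although the documents neither state nor quantify this.

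The primary outcomes are fractions of the clinic population reached, with six clinics per arm. If rurality affects reach, an uneven split shifts the observed contrast in the allocation actually drawn and adds to its variance. With 12 units and no prespecified covariate, there is little room to repair this afterwards, and choosing rurality as a covariate once results are known would be data-driven.

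**Working it through.** The plan gives no figure to reproduce on this point.

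**Inputs from the documents.** 12 clinics (Participants); half per arm (Aim 1); two health systems; allocation within system, blocked on system and size (Randomization of clinics).

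**Assumptions.** 6 clinics per system, allocated 3:3 within each; 4 or 6 rural clinics in all; rurality unrelated to size, except where stated.

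**Formula.** With r rural clinics among the 6 in a system, the chance that k of them go to one arm is C(r,k) × C(6−r, 3−k) / C(6,3), with C(6,3) = 20. Multiplying over the two systems gives 20 × 20 = 400 equally likely allocations.

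**3 rural per system.** Each system gives k = 0, 1, 2, 3 with weights 1, 9, 9, 1 out of 20.
- 3:3 overall: 1×1 + 9×9 + 9×9 + 1×1 = 164 of 400 (41%).
- 4:2 in either direction: 2 × (9×1 + 9×9 + 1×9) = 198.
- 5:1 in either direction: 2 × (9×1 + 1×9) = 36. 6:0 in either direction: 2.
- 4:2 or worse: (198 + 36 + 2)/400 = 59%. 5:1 or worse: 38/400 = 9.5%.

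**Other layouts, same method.** The last column is the chance of a difference of two or more rural clinics.

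| Rural clinics by system | Allocations exactly balanced | Chance |
|---|---|---|
| 3 + 3 | 164/400 | 59% |
| 4 + 2 | 176/400 | 56% |
| 5 + 1 | 200/400 | 50% |
| 6 + 0 | 400/400 | 0% |
| 2 + 2 | 176/400 | 56% |
| 3 + 1 | 180/400 | 55% |
| 4 + 0 | 240/400 | 40% |

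**Odd rural counts.** Under an unrestricted 6:6 draw, the chance of 4:1 or worse with 5 rural clinics is 24%, and the chance of 3:0 with 3 rural clinics is 18%.

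**Unequal systems.** With 4 + 8 clinics and 4 or 6 rural, the chance of a difference of two or more is 43 to 58%, except 0% when the smaller system is all rural and the larger all urban.

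**If rurality tracks size.** Take size-ordered pairs within system, 6 + 6 clinics. If the rural clinics are the smallest 2 (or 4) in each system, no pair is mixed and the chance of imbalance is 0%. If they are the smallest 3 in each, one pair per system is mixed: 4:2 occurs with chance 50% and 5:1 cannot occur.

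**Effect on the contrast (assumed rates, equal clinic sizes, no method effect).** A rural/urban gap of g points shifts the arm contrast by g × (difference in rural count)/6. For g = 5, 4:2 shifts it by 1.7 points and 5:1 by 3.3. For g = 10, the shifts are 3.3 and 6.7. With rural clinics at 8% and urban at 16%, 4:2 gives (4×8 + 2×16)/6 = 10.7% against 13.3%, an odds ratio of 1.29. 5:1 gives 9.3% against 14.7%, an odds ratio of 1.67.

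**The case against.** Blocking on system and size is a defensible choice for 12 clusters, and those two factors may already carry much of the rurality. The size-tracking cases above show that the risk can then be zero. This stands: the documents do not say how rurality overlaps with either factor, so the percentages are conditional. A reader might infer that imbalance is the normal outcome, or that it is avoided only when one system is wholly rural and the other wholly urban. Neither follows. The chance is about even in the mixed layouts, lower for odd rural counts, and it also vanishes under some size patterns.

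A reader might also infer that the comparison is biased by rurality. It is not: over repeated allocations the procedure is unbiased, and analysis by clinic with an overdispersion adjustment lets between-clinic variation enter the standard error. On the assumed 8% and 16%, a clinic-level t-test at 4:2 gives t = 1.12, p = 0.29. Only the rarer 5:1 split gives a nominally significant result (p = 0.018). What remains is a distorted estimate and lost precision in the one draw that is made.

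It might further be inferred that blocking within system requires an even number of clinics from each. The plan asks for half of the 12 overall, and a 7 + 5 split meets that with 4:3 in one system and 2:3 in the other.

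Finally, the multivariable model could include rurality. That is possible, but with no covariate named the plan does not commit to it.

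**Conclusion.** The point holds as an inexpensive improvement to the design, and it does not invalidate the trial. The plan varies rurality on purpose and controls it neither in the allocation nor, by any stated covariate, in the analysis. The size of the risk rests on the assumed layout of clinics: roughly an even chance of a two-clinic difference when 4 or 6 rural clinics are spread over both systems and rurality is unrelated to size, and down to none when rurality follows system or size. How far such a difference would move the result depends on an urban/rural gap in reach that the documents do not give; the rates used here are illustrations. The plan's own reason for blocking, comparable arms, applies equally to this feature.

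**What to change.** Replace the blocking sentence in Randomization of clinics with covariate-constrained randomisation:

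1. State how a clinic is classed as rural, and fix this before the draw.
2. List all 6:6 allocations in which the arms are equal within each system, or differ by at most one clinic where a system has an odd number.
3. Keep those in which the number of rural clinics is equal between arms (even count) or differs by one (odd count), and in which total active patients are close.
4. Retain a list large enough for inference, for example about 100 where feasible, and draw one allocation at random.
5. In the Statistical Analysis Plan, account for the constraint in the primary analysis by using the retained list as the permutation reference.

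With 6 + 6 clinics, the rural condition alone leaves 164 to 240 of the 400 allocations when there are 4 or 6 rural clinics in the layouts tabulated, leaving aside 6 + 0, where all 400 qualify. The size condition will reduce this by an amount that cannot be computed without the clinic sizes. With 100 retained, mirror images included, the smallest two-sided permutation p-value is 2/100 = 0.02. Simply adding rurality as a third block is less practical: with two size classes (an assumption) it makes 2 × 2 × 2 = 8 cells for 12 clinics.

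The cost is a protocol paragraph and a short program, using clinic information that should be in hand before randomisation. Number of Subjects says the clinics are not yet selected. The downside is that the retained list must be archived and used in the analysis.
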